8. GENERAL STATISTICAL CONSIDERATIONS

Additional exploratory analyses of data will be conducted, as deemed appropriate.

Given the nature of this pragmatic study, both efficacy and safety analyses will be performed on randomized patients. As sensitivity analyses, certain efficacy analyses may be repeated by censoring all efficacy data after patients changed the randomized treatment regimen.

All tests of treatment effects will be conducted at a 2-sided alpha level of 0.05, unless otherwise stated.

For continuous measures, summary statistics will include at least the number of patients with data, mean, SD, median, minimum, and maximum. For categorical measures, summary statistics will include at least the number of patients with data, frequency counts, and percentages. For comparisons based on analysis models, the differences will be reported using LS means, along with 95% CIs and p-value. Sometimes, comparison on the summary statistics may be performed and p-values be provided, and such p-values should be viewed as a descriptive measure only. Unless specified otherwise, a two-sample t-test will be used for continuous measurements and Fisher's exact test will be used for categorical measurements. Mean and median will be presented with one more decimal place than the precision of the data. Standard deviation will be presented with two more decimal places than the precision of the data. Minimum and maximum will be presented with the same precision as the original data.

8.1. Treatment Group Comparability

8.1.1. Patient Disposition

The overall study disposition status will be summarized over all enrolled patients. Reasons for screen failures and study discontinuations will be tabulated for each treatment arm and overall population. The data summary will at least contain the following information:

- Number of subjects screened and reason for that

- Number of subjects randomized
- Number and percent of subjects who completed treatment
- Number and percent of subjects who discontinued study and reason for that

Listing will be prepared to present data concerning subject disposition. Listing for screen failure subjects will also be provided along with their screen failure reason. Subjects with study protocol violations summarized by type of violation and listed by treatment and investigative site.

8.1.2. Patient Characteristics

Patient characteristics at baseline (for example, demographics, diabetes history, and comorbidity) will be summarized by treatment arm and overall population. No formal statistical comparisons will be performed. Demographics and baseline characteristics will be listed for all enrolled subjects.

Demographic characteristics will be summarized by treatment groups. For continuous variables such as age, height, weight, income and BMI, the descriptive statistics (n, mean, median, standard deviation, minimum, and maximum) will be reported. For categorical variables such as sex, education, the number and percentage of subjects in each category will be reported.

The Baseline characteristics of include HbA1C, FPG, FSBG, SEITQ and ITSQ, For continuous variables, the descriptive statistics (n, mean, median, standard deviation, minimum, and maximum) will be reported. For categorical variables, the number and percentage of subjects in each category will be reported.

Medical history findings will be summarized by reporting the incidence of subjects with reported MedDRA SOC and preferred terms. Medical history findings will be listed for all enrolled subjects.

8.1.3. Concomitant Therapy

Anti-hyperglycemic concomitant therapy will be summarized at baseline and throughout the study by treatment arm and overall population with coded using the most recent version of the WHO Drug Dictionary. The numbers of subjects using concomitant therapy will be categorized by drug classification (ATC1) and preferred term, and presented by treatment group. By-patient listing will be presented. General concomitant therapy will not be collected or summarized. Anti-hyperglycemic concomitant therapy will be listed for all enrolled subjects.

8.1.4. Treatment Compliance

No patient-reported and HCP-perceived compliance of the treatment will be collected and summarized.

8.2. Efficacy Analyses

Efficacy analyses will be performed on randomized patients.

8.2.1. Primary Analyses

The primary outcome of the study is the change from baseline in HbA1c at Week 24. The null and alternative hypotheses to be tested are as follows:

$$H_0: \hat{\mu}_{\text{arm1}} = \hat{\mu}_{\text{arm2}}$$

$$H_a: \hat{\mu}_{\text{arm1}} \neq \hat{\mu}_{\text{arm2}}$$

where μ is the mean change from baseline at Week 24 for HbA1c (primary endpoint).

In this study, HbA1c will be only measured once post-baseline at Week 24, so missing measurements will not be imputed. In addition to common summary statistics for the change from baseline data, the comparison between 2 treatment arms will be conducted using an analysis of covariate (ANCOVA) model, with change from baseline in HbA1c as response, treatment as fixed effect and baseline HbA1c as a covariate. The 95% CI of LS means difference (insulin analog mid mixture BID – basal insulin analog QD) will be used to make conclusions for the comparison. Specifically, let L and U be the lower and upper limit of this CI. Then,

- If $L > -0.4\%$, the Non-inferiority (NI) of basal insulin analog QD to insulin analog mid mixture BID is established;
- If $L > 0\%$, the superiority of basal insulin analog QD to insulin analog mid mixture BID is established;
- If $U < 0.4\%$, the NI of insulin analog mid mixture BID to basal insulin analog QD is established;
- If $U < 0\%$, the superiority of insulin analog mid mixture BID to basal insulin analog QD is established;

The summary statistics for the change from baseline data includes the number of subjects in each treatment group, mean, SD, median, min and max.

The primary analyses will at least contain n, raw mean, raw SD, adjusted mean. The least-square means (LSmeans) of change from baseline for each treatment group and difference in LSmeans between treatment groups will be presented along with the associated SE and 95% CI.

As a sensitivity analyses, the primary analyses will be repeated by censoring all efficacy data after patients changed the randomized treatment regimen. These analyses will also utilize an ANCOVA model with treatment as factors and the baseline as a covariate. Related plots will also be reported. The primary efficacy endpoints will be listed for each subject at each planned visit.

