Secondary Analyses: For change from baseline in venous fasting plasma glucose (FPG), finger stick blood glucose (FSBG)-based fasting blood glucose (FBG), post prandial glucose (PPG) and blood glucose (BG) excursion, the analyses model will be similar to the primary analyses model, except that the comparison will be based on the treatment contrast p-value from the ANCOVA model.

For percentages of patients reaching treatment goals (<7%) at Week 24 and Week 48, no missing data will be imputed. Count and percentages of patients reaching treatment goals will be summarized, and also be analyzed by a logistic regression model, with logit link function, treatment as fixed effect and baseline HbA1c as continuous covariate.

Insulin dose at each visit will be descriptively summarized by treatment groups by total daily dose (IU and IU/kg).

Safety: The incidence rate of case report form (CRF) collected severe, nocturnal and total hypoglycemic events will be summarized by visit and for the overall study duration. Pairwise comparison between treatment arms will be performed by Fisher's exact test. The overall yearly rates (events/patient/year) of those hypoglycemic events, calculated as, for each patient, the number of episodes times 365.25 and then divided by the patient's treatment duration, will be summarized, and analyzed by a negative-binomial regression model with treatment as fixed effects and log of (patient's treatment duration/365.25) as an offset variable.

Other Analyses: For the medial resource utilization and patient-reported outcome measurements summary statistics will be provided and comparison will be performed by appropriate general test.

Subgroup analysis will be performed for baseline HbA1c, baseline morning PPG, BG excursion, gender, and persistence levels in 2 treatment groups.

2. Schedule of Activities

Table IOQR.1. Schedule of Activities for Prospective Cohorts

eCRF Visit No.:	1	2	3	4	5	6	ET ^a
Week of treatment	0	4	12	24	36	48	ET
Visit Window (days)	–	±7	±7	±7	±14	±14	±14
Informed consent (before procedures/tests)	X						
Demographics	X						
Weight	X	X	X	X	X	X	X
Height	X						
Local urine pregnancy test ^b	X						
Duration of diabetes	X						
Anti-hyperglycemic medications(Non-insulin)	X	X	X	X	X	X	X
Insulin treatment ^c	X	X	X	X	X	X	X
Insulin dose ^d	X	X	X	X	X	X	X
Preexisting conditions/Adverse events ^e	X	X	X	X	X	X	X
Severe, nocturnal and total hypoglycemia events ^f	X	X	X	X	X	X	X

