7.7. Concomitant Therapy

All concomitant therapies that are part of routine care are allowed and can be used during the study.

Only anti-hyperglycemic concomitant therapy will be collected at baseline and throughout the study (Section 2).

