5. SAMPLE SIZE DETERMINATION

The primary objective of the study will be evaluated using the classification method as proposed by Qu and colleagues (2011). With no prior hypothesis specified, the study will be considered a success if a conclusion may be reached by the classification method. With a 1:1 randomization ratio between insulin analog mid mixture BID and basal insulin analog QD, and assuming a non-inferiority margin of 0.4%, no treatment difference between mid mixture BID and basal insulin analog QD, and a common SD of 1.5% for the change from baseline in HbA1c at Week 24, 332 evaluable patients per arm will provide greater than 99% possibility for the study to reach a conclusion for primary analyses with 2-sided alpha level of 0.05. If we assume 20% of the patients will drop out without providing an evaluable post-baseline HbA1c, 415 patients per arm need to be randomized.

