8.5. Subgroup Analyses

Subgroup analyses may be performed on selected outcomes in subgroups of interest. All subgroup analyses will be exploratory in nature. As the interest will be on how different treatment regimens work in a specific subgroup, instead of whether the treatment differences are the same across different subgroups, the subgroup analyses will be performed by analyzing the outcome data in different subgroups, instead of analyzing the outcome data in the whole population with subgroup factors included in the analyses model.

Subgroup analyses will be performed for the primary endpoint and the secondary endpoints to determine whether significant differences exist in primary and secondary endpoint results between subgroups.

These subgroup analyses will be carried out using the subjects from the randomized population.

The list of potential subgroups (with applicable definitions in parentheses) includes, but is not necessarily limited to, the following:

- baseline HbA1c (<8.4% and \geq 8.4%)
- baseline morning PPG (<13.5 mmol/L and \geq 13.5 mmol/L)
- baseline morning BG excursion (<4.4 mmol/L and \geq 4.4 mmol/L)
- baseline body mass index (BMI) (<25 and \geq 25)
- gender (male and female)
- 3-month persistence (discontinued insulin in the first 3 months of treatment or not)

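### The primary ANCOVA is valid but adjusts for baseline HbA1c only; a short pre-specified list of other Visit 1 covariates could modestly tighten the classification interval at little cost

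*SAP*

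**What the plan says.** Protocol 10.3.3.1 and SAP 8.2.1 fit change in HbA1c at Week 24 by ANCOVA with "treatment as fixed effect and baseline HbA1c as a covariate". The Protocol synopsis gives the same model, and the sensitivity analysis that censors after a regimen change uses the same two terms. The 95% CI for mid mixture BID minus basal QD is compared with -0.4%, 0 and 0.4% to give the four possible conclusions. Missing Week 24 values are not imputed in this analysis.

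Other baseline information is available. The Schedule of Activities (Protocol Section 2) records "Duration of diabetes", demographics, height, weight and non-insulin anti-hyperglycemic drugs at Visit 1. Protocol 7.7 confirms the last of these: "Only anti-hyperglycemic concomitant therapy will be collected at baseline and throughout the study". SAP 8.1.2 summarises age, sex and BMI descriptively, and SAP 8.5 uses BMI and gender to define exploratory subgroups. None of these variables enters the primary model. Protocol 7.2 names no stratification factor for randomisation, so the model omits none.

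On sample size, SAP Section 5 plans "with 2-sided alpha level of 0.05", "assuming a non-inferiority margin of 0.4" percent, and "no treatment difference between mid mixture BID and basal insulin analog QD". It takes an SD of 1.5% and 332 evaluable patients per arm, and gives a probability above 99% of reaching a conclusion. It also states: "If we assume 20% of the patients will drop out without providing an evaluable post-baseline HbA1c".

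**The concern.** Every primary conclusion is read from the limits of one interval. In a linear model under 1:1 randomisation, pre-specified prognostic covariates narrow that interval without changing the treatment-policy question, and they cost almost nothing if they turn out not to be prognostic. The variables are already collected, so leaving them out gives up whatever precision they carry.

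The second matter is missing data. With 20% expected to provide no evaluable HbA1c and no imputation, the treatment difference relies on what the model conditions on. Suppose a baseline variable outside the model predicts response and also drives dropout, and does so differently in the two arms. The difference is then biased, and putting the variable in the model removes that part of the bias. Dropout that differs by arm is plausible here: the trial is open-label, the regimens differ in injection frequency, and later treatment is at the discretion of physician and patient (Protocol 7.1 and 7.3). The planned MMRM does not fill this gap, because its only baseline covariate is also baseline HbA1c.

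**Working it through.** **Inputs from SAP Section 5:** SD of change 1.5%, 332 evaluable per arm, margin 0.4%, true difference 0, two-sided alpha 0.05, dropout 20%.

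**Inputs not in the documents (assumed):** extra R2 beyond baseline HbA1c of 0 to 10%; R2 of baseline HbA1c itself of 0 to 40%; strength of the covariate-dropout link, log-odds 0 to 0.7 per SD.

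**Step 1. The plan's own figures.**
- Number randomised: 332/0.8 = 415 per arm, as stated.
- SE = 1.5 × √(2/332) = 0.1164; half-width = 1.96 × 0.1164 = 0.228.
- Reading a conclusion as non-inferiority (NI) in at least one direction, the study fails only if the interval covers both -0.4 and 0.4. That needs a half-width of at least 0.4, so at 0.228 the probability of a conclusion is about 100%, in line with the stated figure above 99%. About 107 evaluable per arm would already give 99%.
- NI in one named direction: Φ(0.4/0.1164 - 1.96) = 93.0%. NI in both directions: 2 × 0.930 - 1 = 86.0%. Neither reproduces a figure above 99%, which supports the reading used.

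**Step 2. Gain from added covariates.** SE is multiplied by √(1 - R2); the equivalent sample size is 332/(1 - R2).

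| Extra R2 (assumed) | Half-width | One-direction NI | Both-direction NI | Equivalent extra patients per arm |
|---|---|---|---|---|
| 0% | 0.228 | 93.0% | 86.0% | 0 |
| 3% | 0.225 | 93.7% | 87.4% | 10 |
| 5% | 0.222 | 94.1% | 88.2% | 17 |
| 10% | 0.216 | 95.2% | 90.3% | 37 |

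The probability of any conclusion is about 100% in every row.

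**Step 3. Why these gains are an upper end.** The 1.5% is the SD of the change itself, before adjustment for baseline HbA1c. If baseline HbA1c explains a share R0 of the variance, the present model's SE is already 0.1164 × √(1 - R0). A further 5% multiplies it by √0.95.

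| R0 (assumed) | Present half-width | Present both-direction NI | With a further 5% | Gain (points) |
|---|---|---|---|---|
| 0% | 0.228 | 86.0% | 88.2% | 2.2 |
| 20% | 0.204 | 94.0% | 95.2% | 1.2 |
| 30% | 0.191 | 96.8% | 97.6% | 0.8 |
| 40% | 0.177 | 98.7% | 99.0% | 0.4 |

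**Step 4. Dropout bias.** Take a standardised omitted covariate with outcome slope 1.5 × √R2, logistic dropout at 20% and true difference 0. The bias is the slope times the between-arm difference in the covariate's mean among retained patients. By simulation that mean is about -0.130 SD at log-odds 0.7 per SD, -0.069 at 0.35 and 0 at 0. For example, with dependence in one arm only and R2 of 5%: 1.5 × √0.05 × 0.130 = 0.044.

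| Dependence of dropout on the covariate | R2 3% | R2 5% | R2 10% |
|---|---|---|---|
| Equal in both arms | 0 | 0 | 0 |
| 0.7 in one arm, 0.35 in the other | 0.016 | 0.021 | 0.029 |
| 0.7 in one arm, 0 in the other | 0.034 | 0.044 | 0.062 |
| 0.7 in opposite directions | 0.067 | 0.087 | 0.123 |

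These are absolute values in HbA1c percentage points, to be set against an SE of 0.116 and a margin of 0.4. With the covariate in the model the bias is about 0.

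**The case against.** The strongest reply is that nothing is broken. ANCOVA on treatment and the baseline value is valid in a randomised trial, protocol and SAP agree on it, and the plan's success criterion is met with about 100% probability with or without more covariates. All of that stands. A reader might infer that the primary model is wrong, or that the trial lacks precision for its stated aim; the documents support neither.

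It is also fair that the size of the gain rests wholly on assumed inputs. The documents contain no R2 and nothing linking these variables to dropout in either arm. Naming BMI and gender as exploratory subgroups does not show that they predict HbA1c change. A reader might infer that the planned estimate is biased because 20% are missing. The omitted covariates produce no bias in the difference if they act on dropout equally in both arms. Nor is the analysis a plain complete-case one: SAP Appendix 1 takes the last post-baseline record up to Visit 4, so an early-termination HbA1c can serve as the Week 24 value.

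Three practical objections can be met. The number of OAM classes is not a defined variable (SAP 8.1.3 plans only ATC1 and preferred-term summaries), so it needs a derivation or should be left out. Extra covariates could lose patients with missing baselines unless a rule prevents it. An SAP-only edit would put the SAP at odds with the protocol.

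The success criterion is not a full answer, however. Protocol 3.2 asks whether mid mixture BID is comparable with basal QD, and that depends on which conclusion is reached. The 93.0% and 86.0% figures describe this, and they are what adjustment can raise.

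**Conclusion.** The point stands as an optional, low-cost improvement and not as an error. If the Visit 1 variables are prognostic beyond baseline HbA1c, adding them shortens the half-width by up to about 0.012 (0.228 to 0.216 at an assumed extra R2 of 10%). Both-direction NI at zero difference then rises by at most about 4 points over the 3% to 10% range. The true gain is probably smaller, because the 1.5% SD gives no credit for baseline HbA1c; if extra R2 is near zero there is no gain.

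The protection against dropout bias is conditional. It is nil under equal dependence, about 0.02 to 0.06 points in the unequal and one-arm cases tested, and up to about 0.12 if the dependence runs in opposite directions. Adjustment does nothing about dropout driven by response after baseline, so it should not be presented as the answer to the 20% missing.

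**What to change.** In SAP 8.2.1, with matching wording in the Protocol synopsis and 10.3.3.1:

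- Fit change in HbA1c on treatment, baseline HbA1c, diabetes duration, baseline BMI, age and sex. Add the number of OAM classes at randomisation only if its derivation is written down.
- Fix the list before any interim analysis (SAP 8.6 allows one after Visit 4, covering the primary objective) and in any case before database lock. No covariate should be selected after outcome data are seen.
- State a simple rule for missing values of the added covariates, such as imputing the overall mean across both arms, so that they remove no patient from the analysis.
- Keep the same 95% CI classification rule, and report the present two-term model as a sensitivity analysis.
- Say whether the list carries over to the Week 48 HbA1c model and the other models that SAP 8.2.2 defines by reference to the primary one.

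The cost is about five degrees of freedom out of about 660, one derivation rule if OAM classes are used, and a documented protocol and SAP change. Under Protocol 10.3.1 the sponsor must decide whether this alters a principal feature and so needs an amendment. No new data are collected. If the sponsor prefers to leave the primary model alone, the minimum is a pre-specified supportive ANCOVA with the same fixed list.

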8.2.2. Secondary Analyses

Missing efficacy values which are HbA1c, FPG, FSBG-based FBG, PPG, BG excursion daily insulin, body weight, SEITQ score will do LOCF. Those missing values will be the last non-missing post-baseline observation up to date of missing values of measurement.

All secondary efficacy endpoints will be listed separately for each subject at each planned visit.

1. For change from baseline in HbA1c at Week 48, the analyses model will be similar to the primary analyses model, and the sensitivity analyses will also be performed.

Also, a mixed-model repeated measures (MMRM) model will be employed to analyze the HbA1c change from baseline at Week 24 and Week 48. This MMRM model will have all post-baseline HbA1c as responses, baseline HbA1c as a continuous covariate, treatment group, Visits (Week 24 or Visit 48), and treatment by visit interaction as fixed effects and patient as a random effect. An unstructured covariance structure will be used to model the correlation within subjects. In case of failure of convergence using unstructured covariance structure, the first-order autoregressive [AR(1)] covariance structure will be used. Missing data will be assumed to be missing at random and therefore maintained as missing. The difference between each of treatment will be assessed by the least-squares means (LSM) difference at Week 24 and Week 48 (alpha=0.05, 2-sided).

A plot of least-squares means for change from baseline by visit for each treatment will be used to display the results of this endpoint.

As sensitivity analyses, the endpoint analyses will be repeated by censoring all efficacy data after patients changed the randomized treatment regimen at Week 48, Ancova analyses for row data and LOCF data at Week 48 separately.

2. For change from baseline in venous FPG, FSBG-based FBG, PPG, BG excursion and bodyweight at Week 24 and Week 48, the analyses will be done similarly to the primary analyses model (ANCOVA for Week 24 and Week 48, and MMRM for Week 24 and Week 48), except for comparison will be based on the treatment contrast p-value from the corresponding analyses model. The sensitivity analyses will also be performed.

Plots of least-squares means for change from baseline by visit for each treatment will be used to display the results of endpoints.

As sensitivity analyses, the endpoint analyses will be repeated by censoring all efficacy data after patients changed the randomized treatment regimen at Week 24 and Week 48, Ancova analyses for row data and LOCF data at Week 24 and Week 48 separately.

3. For percentages of patients reaching treatment goals (<7%) at Week 24 and Week 48, no missing data will be imputed. Count and percentages of patients reaching treatment goals will be summarized (when calculating percentages, the denominator will be the patients with non-missing HbA1c data at Week 24 or Week 48), and also be analyzed by a logistic regression model, with logit link function, treatment as fixed effect and baseline HbA1c as continuous covariate. Adjusted odds ratio, 95% CI and P-value will be presented. Related plot will be reported.

Plots of percentages of patients reaching treatment goals by visit for each treatment will be used to display the results of endpoints.

As sensitivity analyses, the endpoint analyses will be repeated by censoring all efficacy data after patients changed the randomized treatment regimen at Week 24 and Week 48, Ancova analyses for row data and LOCF data at Week 24 and Week 48 separately.

4. Same analyses strategy (refer to above 3) will be used for the composite endpoint of patients reaching treatment goals (<7%) and did not switch from or discontinue study treatment, and did not take rescue medication. Those patients should be without switching or discontinuing study insulin, and without using rescue therapy which will be determined by the investigator following usual standard of care between insulin analog mid mixture BID and basal insulin analog QD treatments.
5. Insulin dose at each visit will be descriptively summarized by treatment groups by total daily dose (IU and IU/kg). The descriptive statistics (n, mean, median, standard deviation, minimum, and maximum) and P-value of a two-sample t-test will be reported.
6. Time to insulin treatment change will be compared between treatment arms by a log rank test. Table and related plot will be reported. Patients who did not have any insulin treatment change up to Week 48 (or up to early discontinuation) will be considered as censored at Week 48 (or time of early discontinuation) with no event. Time to insulin treatment change: Defined as time to any of: insulin treatment

discontinuation, switch, intensification or reduction in frequency. ((date of event/censored - (date of first dose of study drug) + 1.)

Discontinuation: Defined as stopping insulin treatment for 30 days or more.

Switch: Defined as stop the initial insulin therapy and started another insulin therapy of different class.

Intensification: Defined as any of the following: adding meal time insulin in basal insulin analog QD group; changing from BID to TID in insulin analog mid mixture BID group

Reduction in frequency: Defined as any of the following: changing from BID to QD; changing from TID to BID or QD.

Plots of time to event by weeks will be used to display the results of endpoints.

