9.1.2. Secondary Effectiveness Assessments

The following secondary effectiveness measures will be collected at the time shown in the Schedule of Activities (Section 2):

- the change in HbA1c from baseline to 48 weeks
- proportion of patients who achieve HbA1c <7% at 24 and 48 weeks
- venous fasting plasma glucose (FPG) change from baseline at 24 and 48 weeks
- finger stick blood glucose (FSBG)-based fasting blood glucose (FBG), PPG change from baseline at 24 and 48 weeks
- daily insulin dose at 24 and 48 weeks
- body weight change from baseline at 24 and 48 weeks
- the severe, nocturnal and total hypoglycemia incidences and rates during the 24-week and 48-week treatment period
- time to insulin treatment change
- proportion of patients who achieve the HbA1c <7% without switching and discontinuing study insulin, and without using rescue therapy
- the change in Self-efficacy about Insulin Therapy Questionnaire (SEITQ) score from baseline at 48 weeks

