10.3.6. Other Analyses

10.3.6.1. Medical Resource Utilization and Health Economics

10.3.6.1.1. Adherence and Insulin Treatment Pattern

For these measurements, summary statistics will be provided, and comparison will be performed by appropriate general test (see Section 10.3.1).

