9. To compare time to insulin treatment change between insulin analog mid mixture BID and basal insulin analog QD treatments	
9. Time to insulin treatment change: Defined as time to any of: insulin treatment discontinuation, switch, intensification or reduction in frequency
 
Discontinuation: Defined as stopping insulin treatment for 30 days or more.
 
Switch: Defined as stop the initial insulin therapy and started another insulin therapy of different class.
 
Intensification: Defined as any of the following: adding meal time insulin in basal insulin analog QD group; changing from BID to TID in insulin analog mid mixture BID group
 
Reduction in frequency: Defined as any of the following: changing from BID to QD; changing from TID to BID or QD

10. To compare the proportion of patients who achieve the HbA1c <7% without switching and discontinuing study insulin, and without using rescue therapy between insulin analog mid mixture BID and basal insulin analog QD treatments	10. Proportion of patients who achieve the HbA1c <7% without switching and discontinuing study insulin, and without using rescue therapy
11. To compare the patients-reported self-efficacy related to insulin therapy as assessed using SEITQ between insulin analog mid mixture BID and basal insulin analog QD treatments	11. The change in SEITQ score form baseline at 48 weeks

Tertiary/Exploratory	

12. To compare the insulin treatment pattern for
 
 • discontinuation • switch • intensification • reduction in frequency 
between insulin analog mid mixture BID and basal insulin analog QD treatments
	
12. Time to insulin discontinuation, switch, intensification or reduction in frequency
 
Proportion of patients who experience insulin discontinuation, switch, intensification or reduction in frequency during 48 weeks

13. To compare healthcare resource utilization (all-cause and T2DM-related; inpatient, outpatient and ER) between insulin analog mid mixture BID and basal insulin analog QD treatments
	
13. Healthcare resource utilization (all-cause and T2DM-related; inpatient, outpatient and ER) during 48 weeks

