8.3.4. SEITQ = Self-efficacy about Insulin Therapy Questionnaire (SEITQ)

Categorical responses for the each question will be summarized at baseline and endpoint (24 weeks). The change in SEITQ score from baseline at 24 weeks for each treatment group will be presented and P-value will be show in tables. The descriptive statistics (n, mean, median,

standard deviation, minimum, and maximum) and P-value of a two-sample t-test will be reported also.

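### The Week 48 SEITQ secondary endpoint has no named analysis and defaults to an unadjusted t-test, where the plan's own ANCOVA would usually be more precise

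*SAP*

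**What the plan says.** SAP section 3 lists secondary endpoint 11 as "The change in SEITQ score form baseline at 48 weeks", and Protocol 9.1.2 lists "the change in Self-efficacy about Insulin Therapy Questionnaire (SEITQ) score from baseline at 48 weeks".

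SAP 8.2.2 opens with a carry-forward rule that names the SEITQ score: "Missing efficacy values which are HbA1c, FPG, FSBG-based FBG, PPG, BG excursion daily insulin, body weight, SEITQ score will do LOCF". Its six numbered analyses then cover:

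1. HbA1c change at Week 48
2. changes in FPG, FBG, PPG, glucose excursion and body weight
3. HbA1c below 7%
4. the composite responder endpoint
5. insulin dose
6. time to insulin treatment change

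SEITQ is in none of them.

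Three other places bear on SEITQ:

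- **SAP 8.3.4** (exploratory) sets the endpoint at 24 weeks and, for the change at that time, says "P-value of a two-sample t-test will be reported also".
- **Protocol 10.3.6.1.4** gives per-question categorical summaries at baseline and an undated endpoint, and adds that comparisons will be made without naming a test.
- **The Protocol synopsis** sends patient-reported outcomes to a general test. The full text explains that phrase only for insulin treatment pattern, in 10.3.6.1.1: "comparison will be performed by appropriate general test (see Section 10.3.1".

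The default, in SAP section 8 and in Protocol 10.3.1, is "Unless specified otherwise, a two-sample t-test will be used for continuous measurements".

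The primary analysis in SAP 8.2.1 is an ANCOVA "with change from baseline in HbA1c as response, treatment as fixed effect and baseline HbA1c as a covariate". SAP 8.2.2 item 2 applies a similar model "For change from baseline in venous FPG, FSBG-based FBG, PPG, BG excursion and bodyweight at Week 24 and Week 48".

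**The concern.** There are ten secondary endpoints, numbered 2 to 11. Endpoints 2 to 7, 9 and 10 are analysed in SAP 8.2.2, and endpoint 8 (hypoglycemia) in SAP 8.4.4. Endpoint 11 alone has no named analysis, so its test has to be inferred from a general default. The exploratory Week 24 version of the same score does have a named test.

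The inferred test ignores the baseline SEITQ score. That score is collected at Week 0 (Protocol section 2) and its baseline is defined in SAP 7.1. SEITQ is the only change-from-baseline secondary endpoint without baseline adjustment. Insulin dose also gets a t-test, but it is not a change score.

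At stake is the width of the confidence interval for one secondary endpoint, and the clarity of which test was chosen in advance for a self-reported outcome in an open-label trial. The primary HbA1c conclusion is not touched.

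**Working it through.** **The plan's own figures.** The documents give no sample-size or precision figure for SEITQ. The 332 per arm used below is the evaluable number for the primary HbA1c analysis, borrowed for illustration. It reproduces: 332 / (1 − 0.20) = 415 randomized per arm. With SD 1.5, SE = 1.5 × √(2/332) = 0.116 and the 95% half-width is 0.228. This is below the 0.4 margin, in line with the stated probability above 99% of reaching some conclusion.

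**Formulas.** Let s1 be the baseline SD, s2 the Week 48 SD, k = s2/s1 and ρ the correlation between them. Per patient:

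- t-test on change: s1² + s2² − 2ρ·s1·s2
- ANCOVA on baseline: s2²(1 − ρ²)
- difference: (s1 − ρ·s2)², which is never negative
- fractional saving: (1 − ρk)² / (1 + k² − 2ρk), which is (1 − ρ)/2 when k = 1

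**Equal SDs (k = 1), 332 per arm, s1 = 1.** Half-width = 1.96 × √(2 × variance / 332). Equivalent extra patients = 1/(1 − saving) − 1.

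| ρ | Variance, t-test | Variance, ANCOVA | Saving | Equivalent extra patients | Half-width, t-test | Half-width, ANCOVA |
|---|---|---|---|---|---|---|
| 0.3 | 1.40 | 0.91 | 35% | 54% | 0.180 | 0.145 |
| 0.5 | 1.00 | 0.75 | 25% | 33% | 0.152 | 0.132 |
| 0.7 | 0.60 | 0.51 | 15% | 18% | 0.118 | 0.109 |
| 0.9 | 0.20 | 0.19 | 5% | 5% | 0.068 | 0.066 |

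**Unequal SDs, saving in variance.**

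| k | ρ 0.3 | ρ 0.5 | ρ 0.7 | ρ 0.8 | ρ 0.9 |
|---|---|---|---|---|---|
| 0.75 | 54% | 48% | 44% | 44% | 50% |
| 1.25 | 22% | 11% | 2% | 0% | 5% |

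**Cost of the covariate.** Estimating one more parameter inflates the ANCOVA variance by about 1/(N − 4): 0.20% at N = 500, 0.15% at 664 and 0.12% at 830. This shows only where s1 is close to ρ·s2, for example k = 1.25 and ρ = 0.8. No patient is lost, because a change score already needs the baseline.

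**Bounded score.** A simulation of a 5 to 35 sum score (an assumed scoring of the five 7-point items), 332 per arm and 3,000 trials per setting, gave these SEs for t-test and ANCOVA: 0.46 and 0.35 at ρ 0.2, 0.37 and 0.32 at ρ 0.5, and 0.24 and 0.22 at ρ 0.8. Type I error was 4.5% to 5.1% for both.

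**Under carry-forward.** With 664 patients, 20% of Week 48 values replaced at random by Week 24 values and a true difference of 0.2 SD at both times, the ANCOVA to t-test variance ratios at k = 1 were about 0.63, 0.74, 0.86 and 0.95 for ρ 0.3, 0.5, 0.7 and 0.9. In the least favourable case (k = 1.25, ρ = 0.8) the ratio was 1.00. Both estimators averaged 0.20. The gain therefore survives the plan's missing-data rule.

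**The case against.** The strongest reply is that this is largely a preference. The t-test is valid, SEITQ enters no sample-size calculation or decision rule, and simple tests for questionnaires may be deliberate: ITSQ and the Week 24 SEITQ change also get t-tests. This supports a minor rating. It does not explain why endpoint 11 is left unnamed. ITSQ has no baseline assessment in the schedule, so it is no precedent for ignoring one that exists.

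A second reply is that the fallback is less certain than it looks. The Protocol's per-question categorical wording would lead to Fisher's exact test for those item responses. The default sentence also follows text that calls p-values on summary statistics descriptive only. Protocol 10.3.6.1.1, which points to the default, concerns treatment pattern and not SEITQ. All of this is fair. For a continuous change score the t-test remains the natural reading, and it is the test SAP 8.3.4 names at Week 24. The remaining doubt is a further reason to name the analysis.

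Third, calling both estimators unbiased compares them on the same data and does not endorse carry-forward. If the true difference were 0 at Week 24 and 0.2 SD at Week 48, carrying forward 20% would pull either estimate to 0.8 × 0.2 = 0.16 SD. That stands, and it applies to both tests alike.

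Fourth, at least as precise is strictly a large-sample statement. The finite-sample exception is the 0.15% shown above.

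**Conclusion.** The concern holds, as a minor point. Secondary endpoint 11 has no named analysis in the SAP, and the most natural fallback is an unadjusted two-sample t-test. ANCOVA on baseline SEITQ would be at least as precise in large samples and essentially never worse at this trial's size. The variance saving is 5% to 35% with equal SDs and correlations of 0.9 down to 0.3, and 0% to 54% over the wider range of SD ratios. These sizes rest on assumed correlations and SD ratios, because the documents give none, and on 332 per arm borrowed from HbA1c.

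Both methods also assume that the Week 0 questionnaire is completed before the patient knows the allocation. The schedule places both at Visit 1. The issue is lost precision and an unnamed test; choosing the t-test does not in itself add bias, and the primary conclusion does not change.

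**What to change.** Add a numbered item to SAP 8.2.2 for change in SEITQ score at Week 48: ANCOVA with treatment as fixed effect and baseline SEITQ score as covariate, reporting the LS mean difference with its 95% CI. Carry-forward already applies to this score under the section's opening rule; an analysis of observed values can serve as sensitivity. Use the same ANCOVA for the exploratory Week 24 change in SAP 8.3.4, so that the two time points match.

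The cost is SAP wording only. SEITQ is already scheduled at Weeks 0, 24 and 48 and at early termination, its baseline is defined in SAP 7.1, and the model is the one in SAP 8.2.1. The change should be made before the Week 48 data are analysed.
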